6.2.1. Analysis Methodology

Laboratory data will be analysed based on the full analysis set. The data will be summarized by the type of laboratory test.

Unless specified otherwise, percentages are calculated versus the number of participants in the analysis set with non-missing data for the parameter, period (if applicable) and vaccination group under evaluation.

Tabulation of the highest emerging graded abnormalities per period and overall will be provided. Special attention will be given to participants who develop Grade 3 toxicities. For tests that have no grading, tabulations of the worst emerging abnormalities (below/above) will be performed.

6.3. Vital Signs and Physical Examination Findings

Vital sign abnormalities will be determined in accordance with the DMID Vital Signs Toxicity Grading (attachment 2.3.) for adults and adolescents. The worst abnormalities (following vaccination) of vital signs will be tabulated (i.e., showing number and percentage) and listed.

For children, vital signs will be summarized and listed without grading. This summary will be presented per time point and showing the mean, standard deviation, median, Q1, Q3, minimum and maximum. Post-baseline assessments will be allocated to an analysis visit based on the eCRF visit; no visit slotting will be done. Scheduled visits will be used whenever available. If only unscheduled visits are available for a time point, the one closest to the scheduled visit will be used (in case of equidistance, the latest assessment will be selected). The baseline is the last available assessment prior to first vaccination.

It is important to note that a full physical examination is only conducted at screening. At other visits, a brief, symptom-directed examination (including body length/height and weight in

children aged 12 months up to and including 24 months at the time of the boost vaccination) will be performed based on any clinically relevant issues, clinically relevant symptoms and medical history. Therefore, only a listing of participants with worst physical examination findings (i.e., abnormalities) following vaccination will be provided.

REFERENCES

1. Clinical Protocol VAC52150EBL2011: Version 2.0. An open label study to evaluate safety and immunogenicity of an Ad26.ZEBOV booster dose in children previously vaccinated with the Ad26.ZEBOV and MVA-BN-Filo vaccine regimen (15 June 2021).

ATTACHMENTS

1. PERIODIC ALLOCATION OF ADVERSE EVENTS

Solicited AEs are always allocated to the Post boost vaccination period. Unsolicited AEs are allocated to the different periods according to the following rules:

Step 1: Allocation of events to the periods:

Adverse events present in the SDTM database are allocated to periods based on their start date/time. If the start date/time of an event falls between (or on) the start and stop date/time of a period, the AE is attributed to that period (treatment-emergent principle).

Incomplete dates (i.e. time and/or day and/or month and/or year missing):

- In case of partial start or stop dates, the events are allocated to the periods using the available partial information on start and end date; no imputation will be done. If, for instance, for the AE start date only month and year are available, these data are compared to the month and year information of the periods. This rule may lead to multiplication of the event because of its assignment to multiple periods (see below example).

- In case of a completely missing end date (i.e., only for the calculation of duration):

- o In case the AE is not flagged as ongoing, the end date is considered as unknown, therefore the date will remain missing
- o In case the AE is flagged as ongoing the date is imputed by the cut-off date of the analysis for participants still ongoing in the study, and by the end date of the last period for participants who discontinued or completed the trial.

Examples:

Screening period: start date: 14JUN2021 - stop date: 28JUN2021

Post-boost vaccination period: start date: 28JUN2021 - stop date: 19JUL2021

- 1) Adverse event: start date: JUN2021- stop date: 15JUL2021

As the start date only has information about month and year, only this information will be used from the periods (i.e. assuming any day of Jun is possible) and therefore the AE will be assigned to the Screening Period as well as to the Post-boost vaccination Period.

- 2) Adverse event: start date: JUL2021- stop date 14JUL2021

As the AE starts after the Screening Period and after the start of the Post-boost vaccination period, it is only assigned to the Post-boost vaccination period.

Remarks:

- In addition to the date information, time information is considered to allocate AEs to periods, if available.
- The imputation of missing end dates of ongoing AEs will only be used to derive the duration of the event (i.e., to give an indication of the minimum duration). The imputed end dates will not be shown in the data listings.

Step 2: Combination of events:

Overlapping/consecutive events are defined as events in the same participant with the same preferred term which have at least 1 day overlap or for which the start date of an event is 1 day after the end date of the preceding event. Overlapping/consecutive events may be combined into one AE or not, according to the following rules:

- 1) If overlapping/consecutive events start in one of the following periods - Screening or Post boost dose FU (i.e. non-active periods) - followed by an AE in - Post-boost dose (active period) - they are allocated to their respective periods and are considered as separate events.
- 2) In case overlapping/consecutive events start within a single period, they are considered as one and the same AE. The individual events which contribute to this AE are retained as individual records in the ADaM database but are assigned the same onset, period, and total duration.
- 3) In case overlapping/consecutive events start in both an active period followed by a nonactive period, they are allocated to the active period only and are considered as one and the same AE. The individual events which contribute to this AE are retained as individual records in the ADaM database but are assigned the same onset, treatment period, and total duration.
- 4) In case an active period is followed by an active period, and the overlapping/consecutive events start in both periods, they are allocated to their respective period and are considered as separate AEs. The same rule applies for 2 non-active periods.

Remarks:

- 1) Events can only be combined into one and the same AE if their start and stop dates are known.
- 2) In case the completely missing end date is imputed (for period allocation), this date is also considered as a complete date.
- 3) Time is not considered when determining overlap of events.
- 4) Solicited AEs will never be attributed to the Screening Period

Examples:

Screening period: start date: 14JUN2021 - stop date: 28JUN2021

Post-boost dose period: start date: 28JUN2021 - stop date: 26JUL2021

Post-boost dose FU period: start date: 27JUL2021 - stop date: 15AUG2021

Example for the above scenario 1

AE1: start date: 20JUN2021 - stop date: 10JUL2021

AE2: start date: 08JUL2021 - stop date: 18JUL2021

AE1 will be attributed to the screening period and AE2 to the Post-boost dose period.

Example for the above scenario 3

AE1: start date: 18JUL2021- stop date: 28JUL2021

AE2: start date: 28JUL2021- stop date: 08AUG2021

As AE1 starts in the active period (Post-boost dose) and overlaps with AE2 which starts in a non-active period (Post-boost dose FU), this AE is considered as a single AE in the AE analysis starting on 18JUL2021 and ending on 08AUG2021 and is attributed to the post-boost dose period.

2. Toxicity Grading Scale for Healthy Paediatric Participants (older than 3 months) Enrolled in Preventive Vaccine Clinical Trials

Adapted from: DMID° Pediatric Toxicity Tables (November 2007, draft). For adverse events not included in the tables below, refer to the severity criteria guidelines. Reference source not found. Local lab references take preference over the DMD table and the different grades. The abbreviations used in the following tables are: LLN: lower limit of normal; IV: intravenous; ULN: upper limit of normal.

LOCAL REACTIONS				
	Grade 1	Grade 2	Grade 3	Grade 4
Tenderness	Mild discomfort to touch; minimal to no limitation of use of limb	Notable discomfort to touch; Greater than minimal limitation of use of limb	Significant discomfort at rest; Severe limitation of use of limb	Hospitalization or ER visit for treatment
Erythema	<10 mm	10-25 mm	26-50 mm	>50 mm or any grade 3 with hospitalization or ER visit for treatment
Swelling	<10 mm	10-25 mm	26-50 mm	>50 mm or any grade 3 with hospitalization or ER visit for treatment
HEMATOLOGY				
	Grade 1	Grade 2	Grade 3	Grade 4
Hemoglobin for children greater than 3 months and less than 2 years of age	9.0-9.9 gm/dL	7.0-8.9 gm/dL	<7.0 gm/dL	Cardiac Failure secondary to Anemia

Hemoglobin for children greater than 2 years of age	10.0-10.9 gm/dL	7.0-9.9 gm/dL	<7.0 gm/dL	Cardiac Failure secondary to Anemia
Absolute Neutrophil Count	750-1200/mm3	400-749/mm3	250-399/mm3	<250/mm3
Platelets	75,000-99,999/mm3	50,000-74,999/mm3	25,000-49,999/mm3	<25,000/mm3
Prothrombin Time (PT)	1.1-1.2 x ULN	1.3-1.5 x ULN	1.6-3.0 x ULN	>3.0 x ULN
Partial Thromboplastin Time (PTT)	1.1-1.6 x ULN	1.7-2.3 x ULN	2.4-3.0 x ULN	>3.0 x ULN

GASTROINTESTINAL				
	Grade 1	Grade 2	Grade 3	Grade 4
Bilirubin (Fractionated bilirubin test must be performed when total bilirubin is elevated)				
Bilirubin for children greater than 3 months of age (when accompanied by any increase in other liver function test)	1.1- <1.25 x ULN	1.25- <1.5 x ULN	1.5-1.75 x ULN	>1.75 x ULN
Bilirubin for children greater than 3 months of age (when other liver functions are in the normal range)	1.1- <1.5 x ULN	1.5- <2.0 x ULN	2.0-3.0 x ULN	>3.0 x ULN
AST (SGOT)	1.1- <2.0 x ULN	2.0- <3.0 x ULN	3.0-8.0 x ULN	>8.0 x ULN
ALT (SGPT)	1.1- <2.0 x ULN	2.0- <3.0 x ULN	3.0-8.0 x ULN	>8.0 x ULN
GGT	1.1- <2.0 x ULN	2.0- <3.0 x ULN	3.0-8.0 x ULN	>8.0 x ULN
Pancreatic Amylase	1.1- 1.4 x ULN	1.5- 1.9 x ULN	2.0-3.0 x ULN	>3.0 x ULN
Uric Acid	7.5-9.9 mg/dL	10.0-12.4 mg/dL	12.5-15.0 mg/dL	>15.0 mg/dL
Loss of Appetite	Feeding minimally reduced	Feeding reduced by more than 50% of normal for the child	Refusing all feeds	No solid or liquid taken orally for in the last 24 hours; requires intravenous fluids
Diarrhea	Change in consistency of stools OR increase of 1-3 stools over baseline per 24-hour period	liquid/watery stools OR increase of 4 to 6 stools over baseline per 24-hour period	Increase of ≥ 7 stools over baseline per 24-hour period	Requires IV fluid resuscitation and electrolytes repletion OR hypotensive shock

Constipation	Slight change in consistency and/or frequency of stools	Hard, dry stools with a change in frequency	Intestinal obstruction accompanied with abdominal pain	Hospitalization; Severe abdominal distention and vomiting accompanied with severe abdominal pain
Vomiting	1 episode/ day (24h)	2-3 episodes per day (24h)	4-6 episodes per day (24h)	Greater than 6 episodes per day (24h) OR intractable vomiting

ELECTROLYTES				
	Grade 1	Grade 2	Grade 3	Grade 4
Creatinine				
3 Months – 2 Years of age	0.6-0.8 x ULN	0.9-1.1 x ULN	1.2-1.5 x ULN	>1.5 x ULN
2 Years – 3 Years of age	0.7-1.0 x ULN	1.1-1.6 x ULN	1.7-2.0 x ULN	>2.0 x ULN
Hypernatremia	----	145-149 mEq/L	150-155 mEq/L	>155 mEq/L or abnormal sodium AND mental status changes
Hyponatremia	----	130-135 mEq/L	129-124 mEq/L	<124 mEq/L or abnormal sodium AND mental status changes
Hyperkalemia	5.0-5.9 mEq/L	6.0-6.4 mEq/L	6.5-7.0 mEq/L	>7.0 mEq/L or abnormal potassium AND cardiac arrhythmia
Hypokalemia	3.0-3.5 mEq/L	2.5-2.9 mEq/L	2.0-2.4 mEq/L	<2.0 mEq/L or abnormal potassium AND cardiac arrhythmia
Hypercalcemia	10.5-11.2 mg/dL	11.3-11.9 mg/dL	12.0-12.9 mg/dL	>13.0 mg/dL
Hypocalcemia	7.8-8.4 mg/dL	7.0-7.7 mg/dL	6.0-6.9 mg/dL	>6.0 mg/dL
Hypomagnesemia	1.2-1.4 mEq/L	0.9-1.1 mEq/L	0.6-0.8 mEq/L	<0.6 mEq/L or abnormal magnesium AND cardiac arrhythmia
hypoglycemia	55-65 mg/dL	40-54 mg/dL	30-39 mg/dL	<30 mg/dL or abnormal glucose AND mental status changes
Hyperglycemia	116-159 mg/dL	160-249 mg/dL	250-400 mg/dL	>400 mg/dL or ketoacidosis
Proteinuria	Tr-1+ or <150 mg/day	2+ or 150-499 mg/day	3+ or 500-1000 mg/day	4+ or Nephrotic syndrome >1000 mg/day
Hematuria	Microscopic <25 cells/hpf	Microscopic >25 cells/hpf	Gross hematuria	Hospitalization; Lifethreatening consequences

NEUROLOGIC				
	Grade 1	Grade 2	Grade 3	Grade 4
Irritability	Easily consolable; minimal or no interference with activity. Episodes of continuous crying <60 min.	Difficult to console. Episodes of continuous crying >60 min <120 min	Inconsolable, prevents daily activity. Episodes of continuous crying >120 min	Hospitalization or ER visit for treatment
Decreased Activity	Minimal decrease in alertness, minimal or no interference with activity	Some interference with activity, slightly subdued	unable to achieve normal level of alertness, lethargic	ER visit or hospitalization for treatment or life-threatening consequences
Neuropathy/ Lower Motor Neuropathy	----	Mild transient Paresthesia only	Persistent or progressive paresthesia, burning sensation in feet, or mild dysesthesia; no weakness; mild to moderate deep tendon reflex changes; no sensory loss	Onset of significant weakness, decrease or loss of DTRs, sensory loss in "stocking glove" distribution, radicular sensory loss, multiple cranial nerve involvement; bladder or bowel dysfunction, fasciculations, respiratory embarrassment from chest wall weakness.
Myopathy or Neuromuscular Junction Impairment	Normal or mild (<2 x ULN) CPK elevation	Mild proximal weakness and/or atrophy not affecting gross motor function. Mild myalgias, +/- mild CPK elevation (<2 x ULN)	Proximal muscle weakness and/or atrophy affecting motor function +/- CPK elevation; or severe myalgias with CPK >2 x ULN;	Onset of myasthenia-like symptoms (fatigable weakness with external, variable ophthalmoplegia and/or ptosis), or neuromuscular junction blockade (acute paralysis) symptoms
OTHER				
	Grade 1	Grade 2	Grade 3	Grade 4
Fever/pyrexia	38.0 - 38.4 °C or 100.4 - 101.1 °F	38.5 - 38.9 °C or 101.2 - 102.0 °F	39.0 - 40.0 °C or 102.1 - 104.0 °F	Greater than 40 °C or 104.0 °F
Acute allergic reaction	Pruritus without Rash	Pruritic Rash	Mild Urticaria	Severe Urticaria Anaphylaxis, Angioedema
Stomatitis	Mild discomfort	Painful, difficulty swallowing, but able to eat and drink	Painful: unable to swallow solids	Painful: unable to swallow liquids; requires IV fluids
Illness or clinical adverse event (as defined according to applicable regulations)	No interference with activity	Some interference with activity not requiring medical intervention	Prevents daily activity and requires medical intervention	Hospitalization

3. TRANSFORMING ON-SITE ASSESSMENTS AND DIARIES

ASSESSMENTS OF SOLICITED AES INTO ANALYSIS FORMAT

When creating the analysis dataset for solicited AEs, solicited AEs (recorded by day) need to be converted into the format of unsolicited AEs (recorded by event).

All diary data will be considered, as well as any post-dose on-site assessment (scheduled as well as unscheduled) within 8 days after vaccination. For solicited local AEs for which a diameter is measured, the maximum of diameter derived grade and investigator severity will be used.

The start date of the AE will be considered as the date of first occurrence of the solicited AE (both local and systemic). If on subsequent day(s), the same grade is reported, the last reported date is used as the end date of the AE. A new record is created in case the grade of the event changes. If there is a time gap of at least one day between two (or more) occurrences of the particular solicited AE, then the second (and/or next) occurrence will be considered as a new AE. In case no data is reported for a day, this is analyzed as no event reported. If the on-site assessment differs in grade or relatedness (if collected) with the corresponding diary data, only the highest grade and highest level of relatedness per AE will be kept in the analysis database and used in the tables and listings. If relatedness is not collected for an on-site temperature assessment, then relatedness collected on the diary will be used.

The example below shows how the solicited AE should be converted into a format of unsolicited AEs:

Data from the Participant Diary

Participant: 0001

Solicited systemic AE: Headache

	On site assessment	DIARY DATA									
		Day 1 01 Aug21	Day 2 02 Aug21	Day 3 03 Aug21	Day 4 04 Aug21	Day 5 05 Aug21	Day 6 06 Aug21	Day 7 07 Aug21	Day 8 08 Aug21	Grade	Relatedness
Solicited AE	Day 1 01Aug21	01 Aug21	02 Aug21	03 Aug21	04 Aug21	05 Aug21	06 Aug21	07 Aug21	08 Aug21	2	Probable
Grade		2	1	1	0	3	3	1	0	0	0
Relatedness	Doubtful										Probable

The data should be converted and stored in the AE dataset as follows:

Participant No.	AE	Start Date (Char)	Stop Date (Char)	Severity	Relatedness	AEID	Duration
0001	Headache	01Aug21	02Aug21	2	Probable	1	6
0001	Headache	04Aug21	05Aug21	3	Probable	1	6
0001	Headache	06Aug21	06Aug21	1	Probable	1	6

If a solicited AE ends after day 8:

- The stop date of the event is the 'Date of Last day of symptom' as recorded in the eCRF and the 'Maximum severity' after Day 8 as recorded in the CRF. A separate record starting on day 9 is created for this, in case this severity deviates from the previous record.

Of note, to complete the start and end-date based on diary data, the date will be calculated based on the day the AE is reported relative to vaccination and not on the reported date. For example, if the vaccination is on 1st August 2021, and the AE starts on DAY 3, the start date will be set to the 3rd of August 2021 independent of the reported actual date. For the on-site assessments, the actual date as reported in the database will be used.

For the calculation of duration, the first and last day is used, even in case interruptions occurred in between by missing reporting days or 0 grade. In the above example, the 4 records contribute to the same AE, therefore AEID is set to the same value and the duration of the AE is set to 6 for all records.

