^k Diaries will be completed at home by either a project field worker who will visit the participant during daily visits or by the parent/guardian, to document symptoms of solicited local (at the injection site) and systemic adverse events in the evening after the vaccination and then daily for the next 6 days at approximately the same time each day. Day 8 of the diary will be completed at the study clinic by a study doctor or nurse.

^l Serious adverse events and/or special reporting situations that are related to study procedures will be reported from the time a signed and dated ICF is obtained onwards until the end of the study. All other serious adverse events and/or special reporting situations will be reported from the day of vaccination onwards until the end of the study.

^mConcomitant therapies must be recorded from screening onwards until 28 days post-vaccination.

ⁿSerum aliquots for FANG ELISA at all timepoints (D1, D8, D22). Serum aliquot for Ad26 VNA testing at D1.

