6.1.2. Imputation

Missing data will not be imputed. If relationship of AEs to the study vaccine could not be derived (i.e. missing or unknown) it will be considered as unknown, for analysis purposes. Solicited local AEs will be considered as related with the use of study vaccine. Missing relationships will not be imputed.

Period allocation of AEs is defined in Attachment 1.

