6.1.3. Analysis

AEs (solicited and unsolicited) will be tabulated by presenting the number and percentage of participants having at least one of the observed AEs.

The unsolicited AEs will be summarised by System Organ Classification (SOC) and Preferred Term (PT). The solicited AEs will be summarized by class (local, systemic) and PT. For solicited as well as unsolicited AEs, tables focussing on severity and relatedness to vaccine will be created.

SAEs, AEs with fatal outcomes, AEs leading to permanent discontinuation of vaccine, Grade 3 AEs and AESIs will be listed. Tables, summarizing all those parameters will also be created.

For the solicited local and systemic AEs, the duration and time to onset of the events will also be summarized. If a participant experience more than one occurrence of a solicited event, the maximum duration of the events will be used. The time to first onset is defined as:

[date of first onset – reference date+1]

The reference date is the start date of each vaccination period. Duration and time to onset of AEs will be expressed in days.

Summaries, listings, datasets, and/or participant narratives may be provided as appropriate, for those participants who die, or experience a SAE.

The analysis of AEs will be based on MeDRA coded terms as provided in the clinical database.

A listing of all SAEs during the study period will be provided. A listing of all AESIs (if flagged in the database) will be presented as well.

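### Diary days with no data are analysed as event-free on an all-vaccinated denominator, so solicited AE incidence and maximum grade can only be lowered or left unchanged

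*SAP*

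**What the plan says.** SAP Attachment 3 (Transforming on-site assessments and diaries) sets out how daily solicited data become AE records. For a day without data the rule is: "In case no data is reported for a day, this is analyzed as no event reported".

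Three other parts of the SAP determine what that rule does to the tables:

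- Section 6.1.3 (Analysis) summarises AEs as the number and percentage of participants with at least one event.
- Section 2.3.1 (Full Analysis Set) puts all safety analysis on participants with documented vaccine administration. It sets no condition on diary availability.
- Section 6.1.2 (Imputation), which covers AEs, says: "Missing data will not be imputed".

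Duration has its own rule. At the end of Attachment 3, "the first and last day is used, even in case interruptions occurred in between by missing reporting days or 0 grade".

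**The concern.** An unobserved day and a day observed at Grade 0 are different things. Attachment 3 recognises this when it sets the duration rule, but merges the two when it builds events. Analysing an unobserved day as event-free gives it a value, and that sits badly with the statement in Section 6.1.2.

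Safety and tolerability is one of the two primary objectives, and solicited reactions are among its main outputs. A child with no home data remains in the denominator as a non-reactor. Nothing planned would let a reader see how often this happened: the SAP states no diary-completeness table, no non-missing denominator for solicited AEs and no sensitivity analysis. An error that can only make the booster look better tolerated should be removed or made visible, even if it is expected to be small.

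**Working it through.** **Inputs.** About 25 children per age group (SAP 1.4). Eight diary days, Day 1 to Day 8 (SAP Attachment 3). Exact Clopper-Pearson 95% intervals (SAP Section 2). The share of missing days or diaries is not in the documents and is assumed throughout.

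**1. The plan's own figure.** In the Attachment 3 headache example, I read the daily grades as 2, 1, 0, 3, 3, 1, 0, 0 for Days 1 to 8, taking the on-site Grade 2 for Day 1. Duration = last event day - first event day + 1 = 6 - 1 + 1 = 6. This matches the SAP: "the duration of the AE is set to 6 for all records".

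**2. Direction of the error.** Take every 8-day diary with grades 0, 1 or 3 (3^8 = 6,561) and every non-empty pattern of missing days (2^8 - 1 = 255). That gives 6,561 x 255 = 1,673,055 combinations. With missing coded as no event:

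| Participant-level result | Raised | Lowered |
|---|---|---|
| Any event | 0 | 65,280 |
| Maximum grade | 0 | 331,394 |

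The counts show direction only. They are not probabilities, because the combinations are not equally likely in practice.

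**3. Scattered missing days.** Suppose each day is missing independently with probability q. An event lasting d days is lost only if all d days are missing, so reported rate = p(1 - q^d). With p = 40%:

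| q | d = 1 | d = 2 | d = 3 |
|---|---|---|---|
| 2% | 39.2% | 39.98% | 40.0% |
| 5% | 38.0% | 39.9% | 39.99% |
| 10% | 36.0% | 39.6% | 39.96% |
| 20% | 32.0% | 38.4% | 39.68% |

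Short reactions carry almost all of the loss.

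**4. Whole diaries missing.** Here the days are lost together and event length gives no protection. Suppose 10 children report an event and 2 of 25 have no diary:

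- SAP rule: 10/25 = 40.0% (95% CI 21.1-61.3).
- Observed children only: 10/23 = 43.5% (23.2-65.5).
- Both unobserved children had the event: 12/25 = 48.0% (27.8-68.7).

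Each child is 1/25 = 4 percentage points.

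**5. Duration.** In the example, losing any one of Days 2, 3, 4, 5, 7 or 8 leaves the duration at 6. Losing Day 1 or Day 6 gives 5. A group summary can even rise. Durations 1, 1, 1, 1, 3, 3, 4, 5 have median 2.0 and mean 2.4; if two of the 1-day events are missed altogether, the median is 3.0 and the mean 2.8.

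**The case against.** The strongest reply is that little will be missing and the rule is only a convention for building records. Diaries are completed by a field worker, or by the parent with field-worker checks (Protocol 8.1.3). On-site assessments are also used. Staff complete the last entry: "Day 8 of the diary will be completed at the study clinic by a study doctor or nurse" (Time and Events Schedule, footnote k). Most of Section 6.1.2 concerns missing relatedness, so its opening sentence may not have been aimed at diary days. The study is descriptive, and a shift of 3.5 points (43.5 - 40.0) lies well inside an interval 40.2 points wide (61.3 - 21.1).

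Much of this stands. It limits the likely size and shows why the size cannot be fixed from the documents. It does not change the direction of the error, and it does not supply a table that would show the reader how complete the diaries were. The sentence in 6.1.2 is also unqualified as written.

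Three stronger readings are tempting, and the documents do not support them.

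- *Durations are lowered too.* Not uniformly: interior missing days are counted within the event. Only a missed first or last event day, or a wholly missed event, shortens a child's duration. Separately, Attachment 3 says that after a gap of at least one day "then the second (and/or next) occurrence will be considered as a new AE", and Section 6.1.3 says "the maximum duration of the events will be used". On that reading the example gives 3 days (Days 4 to 6), not 6. That inconsistency needs reconciling in its own right, but it is not this point.
- *Missing Day 8 data are built in, because the visit may fall as late as Day 11.* Nothing says that a Day 8 entry completed at a later visit is left blank or analysed as unreported. Attachment 3 dates diary entries by their day relative to vaccination.
- *The laboratory analysis sets a rule that the solicited AE analysis breaks.* Section 6.2.1 does say that "percentages are calculated versus the number of participants in the analysis set with non-missing data", but for laboratory data only. A child with one of two post-booster samples would still be counted there. It shows that the SAP uses a non-missing denominator elsewhere, no more than that.

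**Conclusion.** The point holds for participant-level incidence and maximum grade of solicited AEs, which the rule can lower or leave unchanged but never raise. It does not follow that every severity category falls: the share of children with a maximum of Grade 1 or 2 can rise when a worse day is missed.

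The size rests wholly on an assumed missing rate. For scattered missing days at 2% to 20%, the loss on a true 40% rate is 0.8 to 8.0 points for a 1-day event and at most about 0.3 points for a 3-day event. For lost diaries, each affected child in a group of 25 leaves up to 4 points unresolved. If diaries prove nearly complete, the effect will be negligible, but the planned outputs would not show that. The SAP should be changed before analysis. This does not call the study's design into question.

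**What to change.** In SAP Attachment 3, replace the sentence with: a day with neither diary nor on-site data is missing, not Grade 0. Cross-refer to it from Section 6.1.2. Then in Section 6.1.3:

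1. Base solicited AE percentages on participants with at least one solicited assessment of that term after leaving the clinic on Day 1, and still count any child with an event recorded on site. A requirement for any post-booster assessment would exclude almost nobody, because every child should have solicited events recorded at the 30-minute observation (Protocol 3.1 and 8.1.3).
2. Tabulate, by age group, the number of children with any missing diary day.
3. Add one sensitivity table, for incidence only, that counts children with missing days and no recorded event as having the event. This is an upper bound. It also covers partly missing diaries, which the new denominator alone does not.

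The cost is SAP wording and programming, with no new data collection. Denominators will vary slightly between terms. Keeping children with an on-site event but no later data leans the percentage slightly upward, which the completeness table makes visible.
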